##### 6.3.2.2. Concomitant medications:

No data will be imputed.

##### 6.3.2.3. Other safety end points

No data will be imputed.

#### 6.4. Visit Windows

Visits will be performed every 21 ( $\pm$  3) days or 28 ( $\pm$  4) days after each infusion until week 51, or 52 (i.e., study termination visit), depending on the patient's treatment schedule. All visits will be summarized according to the nominal visit.

For PK data analysis see [Section 9.1](#).

#### 6.5. Pooling of Centers

Data from all centers will be pooled together.

#### 6.6. Subgroups

Subgroup analyses by age and treatment schedule are planned to be performed for the primary and secondary efficacy endpoints and for safety endpoints, including AEs (infusional AEs and treatment-emergent AEs). Additional subgroup analyses by sex, race are planned to be performed for the primary efficacy endpoint. Subgroup analysis by region will not be performed because only sites of USA enrolled subjects.

This document is confidential.

#### 6.6.1. Age

The age categories for the subgroup analysis are

- children (2 to 11 years, inclusive)
- adolescents (12 to 17 years, inclusive)
- adults (18 to 70 years, inclusive).

The age categories will be consistent for all subgroup analyses with the exception of PK, where blood samples will only be taken from adults.

Age will be the age recorded at screening (initial visit). The same age will be used per patient during the entire study (i.e., if a patient's age changes from 17 to 18 years during the study, the patient will remain in the age category of 12 through 17 years during the entire study).

#### 6.6.2. Treatment Schedule

The treatment categories for the subgroup analyses will be 21 days and 28 days.

#### 6.6.3. Race

The race categories for the subgroup analyses will be White and pooled group of all other races.

## 7. Demographic, Other Baseline Characteristics and Medication

### 7.1. Patient Disposition and Withdrawals

Patient disposition will be summarized by presenting the number and percentage of patients eligible for the study, treated with study medication and completed or discontinued from the study together with the primary reason for premature termination. The number of patients enrolled at each site will be presented. The summaries will be done by dosage interval (21- or 28-day) and overall for the 'All patients enrolled set'.

Major protocol deviations will be summarized for patients in FAS by dosage interval (21- or 28-day) and overall.

A further summary table will be presented detailing the number of patients in each analysis set. Furthermore, the number of patients excluded from each analysis set will be summarized by reason for exclusion. These summaries will be presented by dosage interval (21- or 28-day) and overall. All data will be summarized and listed.

### 7.2. Demographic and Other Baseline Characteristics

Demographic (age, gender, weight at baseline, race and ethnicity) and baseline characteristics (child-bearing potential status, tolerance of previous IgG treatment and antibody response to pneumococcal vaccination (if available)) will be presented in a summary table and a listing. The summary table will be based on the FAS, PPS and PK Evaluation set and will be done by dosage interval (21- or 28-day) and overall.

Age will be summarized as both a continuous variable and using the subgroup categories defined in [Section 6.6.1](#).

Separate summaries will also be presented by age category for FAS.

All data will be listed.

### 7.3. Medical History and Concomitant Diseases

Medical history terms (including infection history) will be coded using MedDRA to give a preferred term (PT) and a system organ class (SOC) term for each medical history term. At the end of the study, medical history will be recoded applying the latest available MedDRA version available at this time point.

#### 7.3.1. PID history

PID history will be summarized by the number and percentage of patients within each SOC and PT. Time since disease diagnosis will be presented by means of descriptive statistics.

The summary table will be based on the FAS and will be done by dosage interval (21- or 28-day) and overall. All data will be listed.

#### 7.3.2. Non PID Medical History

Medical history (previous and concomitant diseases) will be summarized by the number and percentage of patients within each SOC and preferred term. This summary will be done overall based on the FAS.

This document is confidential.

Medical history terms with ongoing ticked 'No' will be considered as previous diseases, with ongoing ticked 'Yes' as concomitant diseases.

Summaries will be based on the FAS. All data will be listed.

#### **7.4. Other Baseline Characteristics**

Prior IVIG therapy for treatment of PID (taken in the last 3 months prior to start of this study) will be coded using WHO-DD using Anatomical Therapeutic Chemical (ATC) Classification Level 2 and 3 plus any applicable sorting (e.g. type of therapy and/or setting). The latest available version of WHO-DD available at the end of study will be used.

The number and percentage of patients with prior PID therapies will be presented by ATC Levels 2 and 3, and the preferred term.

In addition, patients currently receiving IVIG infusions/other medications yes/no, number of IgG trough levels of  $\geq 6$  g/L within 12 months prior to enrolment and patient's baseline IgG levels will be summarized,

The summary tables will be based on the FAS and will be done by dosage interval (21- or 28-day) and overall. All data will be listed.

#### **7.5. Medication**

Rules for discriminating prior/concomitant medications are defined within [Section 6.2.17](#).

Medication will be coded using WHO-DD using Anatomical Therapeutic Chemical (ATC) Classification Level 2 and 3 plus any applicable sorting (e.g. type of therapy and/or setting). The latest available version of WHO-DD available at the end of study will be used.

The number and percentage of patients taking previous and concomitant other medications (excluding immunoglobulins) will be summarized overall by ATC Levels 2 and 3.

The number and percentage of patients taking premedications, to avoid AEs occurring in conjunction with the infusion of IVIg products during the study will also be summarized overall by ATC Levels 2 and 3. These will be identified by a review of the coded medications and include antihistamines, antipyretics, and/or steroids with indication - prophylaxis.

The number and percentage of patients taking previous antibiotic medications will be summarized overall by ATC Levels 2 and 3. Concomitant antibiotic medication is one of the secondary efficacy endpoints and is described in the [Section 8.2.10](#).

The number and percentage of patients taking prohibited medication or treatment during the study will be summarized overall by ATC Levels 2 and 3. Prohibited medication or treatment includes the use of other polyclonal IgG (SCIG or IVIg) between the first infusion of KIG10 and the study termination visit. High dose steroids (oral and parenteral, daily  $\geq 0.15$  mg of prednisone equivalent/kg/day), and other immunosuppressive (including monoclonal antibodies)/cytotoxic drugs are prohibited during the study period except when required for emergency use, and their use must be recorded. These will be identified by a review of the coded medications.

All presentations will be done based on the FAS.

All available information will be listed.

This document is confidential.

## 8. Efficacy

Efficacy endpoints are based on data from different sources: eCRF, patient diary and questionnaires. The summaries will be based on the FAS.

All data will be listed.

### 8.1. Primary Efficacy Endpoint and Analysis

#### 8.1.1. Definition

Incidence rate (i.e., the mean number of acute serious bacterial infections per patient-year) of acute serious bacterial infections (bacterial pneumonia, bacteremia/sepsis, bacterial meningitis, visceral abscess, osteomyelitis/septic arthritis) according to FDA (1) and EMA (2) guidelines and the criteria described in the relevant FDA (1) guidelines.

#### 8.1.2. Main Analysis

Primary analysis of the primary endpoint will be performed on the FAS. Primary efficacy will be analyzed using a Poisson model using as offset the length of the observation period after the start of treatment per patient. The unit of measurements of time is years. The estimate and 1-sided 99% upper confidence limit will be reported. Efficacy will be claimed if this limit is less than 1.0.

Any intra-patients correlations of acute serious bacterial infections are not considered to follow a conservative approach for the infection rates.

SAS code:

```
proc genmod;
  model [Number of Infections] = / dist=poisson link=log
  offset=log(observation period after the start of treatment per patient
  in years) alpha=0.02 ;
run;
```

The primary efficacy analysis will be tested overall, e.g., without separation by dosing interval.

A per-subject primary endpoint analysis dataset will be derived from AE data. The following terms will be searched in AE preferred term to determine if an acute serious bacterial infection occurred: bacterial pneumonia, bacteremia/sepsis, bacterial meningitis, visceral abscess, osteomyelitis/septic arthritis. For each subject, the number of acute serious bacterial infections will be derived.

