### 3.4. Brief Description

This is a phase III, open-label, prospective, single arm, historically controlled, multicenter study to evaluate efficacy, safety, and PK of Klg10 in patients, aged 2 to 70 years at the time of screening, and affected by PID.

Enrollment of the 2 to 11 year old pediatric patients will be delayed until acceptable safety and efficacy of Klg10 for the PID treatment of adolescents (12 to 17 years) or adults are demonstrated.

All patients will receive an intravenous infusion of Klg10 every 21 days or 28 days (depending on the treatment regimen determined by their attending physician) for a period of 48 weeks at the study site. The first infusion of Klg10 will mark the beginning of the investigation period and enrollment.

Visits will be performed every 21 ( $\pm 3$ ) days or 28 ( $\pm 4$ ) days after each infusion until week 51, or 52 (i.e., study termination visit), depending on the patient's treatment schedule (please refer to the table below).

Procedure 28-day regimen (21-day regimen in parentheses)	Timing	Comments
Screening	Day -28 to day 0 (Day -21 to day 0)	up to 3/4 weeks prior to the first infusion
Infusion 1	Week 1, Day 1 Baseline	Enrollment
Infusion 2-4 (Infusion 2-4)	Week 4 to 12 (Week 3 to 9)	
PK Assessment	Infusion 5, Week 16 (Infusion 7, Week 18)	For PK Evaluation Set only
Infusion 6 to 13 (Infusion 6 to 17)	Week 20 to 48 (Week 15 to 48)	
Study termination visit: 28 days after last infusion (21 days after last infusion)	Week 52 (Week 51)	Up to 4 weeks after the last study infusion

This document is confidential.

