### 3.6. Determination of Sample Size

A sample size of at least 40 evaluable patients is considered a sufficient number to evaluate the primary study endpoint according to the relevant FDA (1) and EMA (2) guidelines. A sample size of 40 achieves 90% power to reject the null hypothesis of an acute serious bacterial infection incidence rate greater or equal to 1.0 by means of a 1-sided test and a Type 1 error of 0.01 assuming a true underlying rate of acute serious bacterial infections of 0.49 per year (assuming a Poisson process). CCI [REDACTED] Thus, about 50 patients are planned to be screened to account for drop outs (10%) and screening failures (10%).

Within the planned CC patients, up to CCI pediatric patients will be enrolled in order to collect preliminary evidence in this population.

The enrollment of 2 to 11 year old patients will be delayed until the efficacy (in terms of IgG trough levels) and the safety of the product have been demonstrated in at least 10 adolescent ( $\geq 12$  years) or adult patients with at least 3 infusions (i.e., 3 months of exposure).

This document is confidential.

Approximately [REDACTED] adults of the [REDACTED] patients will have a PK profile analyzed before and after the 5th study infusion (28-day infusion schedule) or 7th infusion (21-day infusion schedule) to ensure data collection from at least 20 evaluable adult patients.

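### The primary 99% upper limit is coded as a Wald limit, which is wider than the exact Poisson limit at every count of 1 or more and at some person-time totals costs one allowable event

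*SAP*

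**What the plan says.** SAP 8.1.2 runs the primary analysis on the FAS, with each patient's observation time in years as the offset. The decision rule is "The estimate and 1-sided 99% upper confidence limit will be reported. Efficacy will be claimed if this limit is less than 1.0". The code fits "model [Number of Infections] = / dist=poisson link=log" with the level given as "in years) alpha=0.02", which is a two-sided 98% interval and hence a 1-sided 99% upper limit. The SAP does not say how the limit is to be calculated. Protocol 10.3 gives the same rule in its visible text, also without naming a method.

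SAP 3.6 gives the planning figure: "A sample size of 40 achieves 90% power to reject the null hypothesis". The null value is 1.0 per year or more, the test is 1-sided at level 0.01, and the alternative is 0.49 per year with Poisson counts.

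Observation time is the termination date minus the first infusion date plus 1 (SAP 6.2.20), and days are divided by 365 (SAP 8.1.3). SAP 3.4 places the termination visit "28 days after last infusion (21 days after last infusion", the bracketed interval being for the 21-day schedule. The attending physician determines the schedule (SAP 3.7), so the split is not fixed.

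**The concern.** A Wald limit on the log scale is a large-sample approximation. Here it errs in one direction only: at every count of 1 or more it lies above the exact Poisson limit. The exact limit is itself conservative, so the extra width adds no protection against a false claim.

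Two things are at stake. First, the success boundary can move by one event: at some totals of patient-years the exact limit would allow the claim and the coded limit would not. Second, the reported limit is too wide at the low counts an effective product would produce.

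**Working it through.** **Inputs.** z(0.99) = 2.326; success if the limit is below 1.0; true rate 0.49 per patient-year; 1-sided type I error 0.01 (SAP 3.6 and 8.1.2). Let x be total events and T total patient-years.

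**Formulas.**
- Coded (Wald) limit: (x/T) × exp(2.326/√x)
- Exact limit: chi-square(0.99; 2x+2) / (2T)
- Cut-off c: the largest x whose limit is below 1.0
- Power: P(X ≤ c) for X Poisson with mean 0.49T
- Actual type I error: the same probability with mean T

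**Reproducing the plan's figure.** At T = 40.0 both limits give c = 25. Power is 90.5% and actual type I error 0.0076. A normal approximation with the null variance gives 90.05%. The stated 90% is correct.

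**Width.** The limit multiplied by T is also the number of patient-years that x events need in order to pass:

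| x | Wald | Exact | Ratio |
|---|---|---|---|
| 1 | 10.24 | 6.64 | 1.54 |
| 3 | 11.49 | 10.05 | 1.14 |
| 10 | 20.87 | 20.14 | 1.04 |
| 24 | 38.59 | 38.08 | 1.013 |
| 25 | 39.81 | 39.31 | 1.013 |

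The ordering holds at every count from 1 to 200,000. At T = 40, one event would be reported with a limit of 10.24/40 = 0.256 instead of 6.64/40 = 0.166.

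**Where the decisions differ.** For a given x the rules disagree when T lies between the two thresholds, for example between 39.31 and 39.81 for 25 events. Near there each such gap is about 0.50 patient-years wide, and successive Wald thresholds are 39.81 − 38.59 = 1.22 apart, so the gaps cover roughly 0.50/1.22 = 41%. Counted directly over 36 to 48 patient-years, the share is 40% and the mean power difference is about 3.2 points.

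| T | Coded c | Exact c | Coded power | Exact power | Coded type I error | Exact type I error |
|---|---|---|---|---|---|---|
| 39.31 | 24 | 25 | 88.1% | 91.8% | 0.0060 | 0.0100 |
| 39.62 | 24 | 25 | 87.4% | 91.2% | 0.0053 | 0.0088 |
| 39.81 | 24 | 25 | 86.9% | 90.8% | 0.0049 | 0.0082 |
| 40.0 | 25 | 25 | 90.5% | 90.5% | 0.0076 | 0.0076 |
| 40.5 | 25 | 25 | 89.5% | 89.5% | 0.0062 | 0.0062 |
| 41.0 | 25 | 26 | 88.4% | 91.9% | 0.0050 | 0.0083 |
| 42.0 | 26 | 27 | 90.0% | 93.1% | 0.0055 | 0.0091 |

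(The rows marked 39.31 and 39.81 are at 39.3096 and 39.8082.)

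**How the plan could reach such totals.** A 28-day completer contributes 336 + 28 + 1 = 365 days and a 21-day completer 336 + 21 + 1 = 358. Forty completers with k on the 21-day schedule give T = 40 − 7k/365. That is 39.827 at k = 9, where the rules agree, and 39.808 at k = 10, where they part. From k = 37 (T = 39.290) the exact rule also drops to 24 events, and power is about 88% under both.

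**Adding FAS time.** SAP 3.6 screens about 50 to allow for 10% screening failures and 10% dropouts, so about 45 are treated. Assume 40.5 complete, 4.5 drop out and half are on the 21-day schedule. Completers then give 40.5 − 20.25 × 7/365 = 40.11 patient-years. The timing of dropout is an assumption:

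| Mean dropout time | T | Coded power | Exact power |
|---|---|---|---|
| 0.1 y | 40.56 | 89.3% | 92.6% |
| 0.25 y | 41.24 | 91.5% | 91.5% |
| 0.5 y | 42.36 | 92.6% | 92.6% |

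**The case against.** A reader might infer that with 10 or more of 40 patients on the 21-day schedule the trial misses its stated 90% power. The documents do not support that:

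- It presumes 40 completers and no other person-time. The primary analysis is on the FAS, which counts every dosed patient's time including dropouts, and at 41.24 or 42.36 patient-years coded power is above 90%.
- The figure of 10 depends on day counting. It becomes 5 without the added day, 9 with 365.25 days per year and 3 with both changes. The visit windows of ±3 and ±4 days shift it again.
- The Wald limit is not the only cause. Both rules give 89.5% at 40.5 patient-years and about 88% just below 39.31. That is the discreteness of the count.

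These objections stand, and they confine the point to the choice of limit.

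It is also fair to say that the coded rule is conservative, so no false claim is at risk, and that at low counts both limits are far below 1.0, so the decision does not change there. Both are true. They limit the seriousness but do not justify a limit wider than one that already holds its level.

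Two further objections carry less weight. The supportive analyses in SAP 8.1.4 are redacted and may include an exact limit, but a supportive analysis would not change the primary rule as coded. That the limit is Wald is read from the software default, since the SAP does not name it; but no other method is requested in the visible code.

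**Conclusion.** The concern holds as one about the choice of limit. As coded, the primary upper limit is wider than the exact Poisson limit at every count of 1 or more. At about 40% of totals between 36 and 48 patient-years it accepts one event fewer, at a cost of about 3 to 4 points of power near the planned size. Where the rules differ, the coded rule spends only about 0.005 to 0.006 of the 0.01 allowed.

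The sample-size statement is not wrong: it is correct at 40.0 patient-years under either limit. Whether coded power ends below 90% depends on the schedule split, the day count and the dropout time in the FAS, none of which the documents fix. The exact limit does not guarantee 90% either; for any count of 1 or more it is simply never wider and never less powerful.

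This rests on the Poisson assumption of SAP 3.6, a true rate of 0.49 and the GENMOD default interval. It is worth correcting, but it does not threaten the validity of a positive result. The zero-event case, where the Wald limit does not exist, is a separate matter.

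**What to change.** In SAP 8.1.2, define the primary 1-sided 99% upper limit as the exact Poisson limit, chi-square(0.99; 2x+2) / (2 × patient-years), where x is the total number of acute serious bacterial infections in the FAS and patient-years are totalled as in SAP 8.1.3. Keep the Poisson model for the point estimate, and name the limit in the text so that it does not depend on a software default.

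The drafting cost is one line of text and one of code. The small downside is that the change slightly loosens the success rule of an open-label, single-arm trial that, by SAP 6.6, had already enrolled patients. It should therefore be made in a documented SAP amendment, with the reason stated, before database lock and before the event count is reviewed. Choosing the limit after seeing the count would undermine the claim.

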#### 4.7 DATA MONITORING COMMITTEE

The DSMB will be responsible for safeguarding the interests of trial participants, assessing the safety and efficacy of the interventions during the trial, and for monitoring the overall conduct of the clinical trial. The DSMB will provide recommendations about continuing or terminating the trial on ethical grounds.

The DSMB will be advisory to the Sponsor clinical trial team. The sponsor clinical trial team will be responsible for promptly reviewing the DSMB recommendations, to decide whether to continue or terminate the trial and to determine whether amendments to the protocol or changes in study conduct are required.

The DSMB will be asked to review the full documentation for specific AEs and determine whether they meet the criteria for acute serious bacterial infections (as described in Section 8.1.1, Serious Bacterial Infections), defining the study's primary endpoint. Furthermore, the DSMB will be asked to review safety and efficacy data (in terms of IgG trough levels) on at least 10 adolescent or adult patients with 3 infusions (i.e., 3 months of exposure). After a positive evaluation, Kedrion intends to continue studying the efficacy and safety of Kig10 in the young age group of PID patients (children < 12 years of age).

DSMB will also review data that are indicative of intravascular hemolysis.

The DSMB will be independent from Sponsor and Investigators providing their expertise and recommendations. Functions and organization of DSMB are described in the DSMB Charter.

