## 8. EFFICACY PHARMACOKINETIC, AND SAFETY VARIABLES

### 8.1 EFFICACY VARIABLES

#### 8.1.1 SERIOUS BACTERIAL INFECTIONS

If an acute serious bacterial infection is suspected, the patient must be evaluated for the infection according to the methods described in the *FDA Guidance for Industry: "Safety, Efficacy and Pharmacokinetic Studies to Support Marketing of Immune Globulin Intravenous (Human) as Replacement Therapy for Primary Humoral Immunodeficiency; June 2008,"* as defined below.

Items in **bold** are considered essential diagnostic features.

The DSMB will be responsible for review the full documentation for specific AEs and determine whether they meet criteria for acute serious bacterial infections. The procedure to complete this activity will be detailed in the DSMB Charter.

All acute serious bacterial infections will be recorded in the eCRF.

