- *Symptoms:* abdominal pain, anorexia, weight loss, cough/pleuritic chest pain (hepatic abscess), rigors (seldom present)
- *Physical findings:* intermittent fevers (temperature > 38°C oral or > 39°C rectal); abdominal tenderness; palpable mass; hepatomegaly; jaundice
- *Laboratory tests:* **positive Gram stain and/or culture from the infected site, with isolation of an appropriate pathogen;** positive blood culture; leukocytosis with accompanying left shift; differential WBC count of > 10% immature (band) neutrophils, elevated serum amylase concentration (pancreatic abscess); elevated alkaline phosphatase concentration (hepatic abscess) pyuria in renal abscess
- *Imaging studies:* **typical findings on ultrasound, CT scan, MRI scan, or radionuclide scan**

a Two of the following should be present to make the diagnosis of sepsis in adults: temperature > 38°C oral/ > 39°C rectal or < 36°C oral or < 37°C rectal; heart rate > 90 beats/minute; respiratory rate > 20 breaths/minute, or PaCO2 < 32 mm Hg; WBC count > 12,000/mm^3, < 4,000/mm^3, or > 10% immature (band) forms. For pediatric patients, the definition of sepsis using age-specific criteria is recommended by the International Consensus Conference on Pediatric Sepsis (Pediatric Crit Care Med 2005; 6(1):2-8).

b Indwelling catheter or vascular access device-related blood-borne infections are not included because evidence is lacking that these are preventable with IVIg replacement therapy. For patients without indwelling catheters or vascular access devices, a single blood culture positive for a pathogenic organism will meet the diagnostic criteria

for bacteremia (multiple blood cultures are typically obtained in cases of suspected bacteremia/sepsis, as per standard medical practice, and the finding of a single positive culture should prompt additional confirmatory cultures). Patients meeting criteria for positive blood culture but without 2 or more of the sepsis criteria listed above will be classified as having bacteremia.

- c A blood culture positive for growth of *Streptococcus pneumoniae*, *Neisseria meningitidis*, or *Haemophilus influenzae*, in combination with CSF leukocytosis and/or glycorrhachia, can serve to confirm the diagnosis of acute bacterial meningitis.

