- d For the diagnosis of pneumonia in adults, commonly at least 2 of the listed symptoms and/or signs should be present in conjunction with at least one laboratory and one imaging studies diagnostic element. However, for the purposes of counting serious infection episodes in a clinical trial of IVIg, the finding of a new pulmonary infiltrate with consolidation on chest x-ray is considered sufficient. To establish the diagnosis of bacterial pneumonia for pediatric patients, most of the same diagnostic criteria listed may be used, with the following exceptions: Because pediatric patients may not produce a sputum specimen for culture, blood cultures or serology may be substituted to identify the etiologic bacterial pathogen. In infants age 3 to 24 months, fever is defined as a rectal temperature > 38.3°C (101°F). In children > 2 years, fever is more commonly defined as a rectal temperature > 38°C (100.4°F). In pediatric patients, elevations of WBC counts > 15,000/mm^3 are frequent but could be variable in patients with bacterial pneumonia, or leukopenia with WBC count < 5000/mm^3 may be observed, usually associated with severe infection.
- e A deep expectorated sputum gram stain is recommended to demonstrate the presence of microorganisms on examination of 10-20 oil immersion microscopic fields and < 10 squamous epithelial cells and > 25 polymorphonuclear leukocytes at 10X low power magnification to determine suitability of sputum culture.

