### 2.2. Timings of Analyses

An interim pharmacokinetic (PK) analysis is planned after at least [REDACTED] patients with complete intense PK sampling before and after infusion 5 for 28 days schedule or infusion 7 for 21 days schedule. An interim PK report will be produced by the study PK scientist.

The primary analysis of safety and efficacy and pharmacokinetics is planned after all patients complete the final study visit or terminate early from the study.

An independent Data and Safety Monitoring Board (DSMB) will review the full documentation for specific AEs and determine whether they meet the criteria for acute serious bacterial infections (as described in protocol Section 8.1.1, Serious Bacterial Infections), defining the study's primary endpoint. Furthermore, DSMB will be asked to review safety and efficacy data (in terms of IgG trough levels) on at least [REDACTED] adolescent or adult patients with [REDACTED] infusions (i.e. [REDACTED] months of exposure). After a positive evaluation, Kedrion intends to continue studying the efficacy and safety of Klg10 in the young age group of PID patients (children < [REDACTED] years of age). DSMB will also review data that are indicative of intravascular hemolysis.

The timing and content of the DSMB reviews will be described in the DSMB charter.

This document is confidential.

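### The primary endpoint count is programmed from a search of coded AE terms, not from the DSMB determination that both documents prescribe, so the primary rate can be miscounted

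*SAP*

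**What the plan says.** Four places assign the decision to the DSMB.

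- Protocol 4.7: the DSMB examines the full documentation of specific AEs to "determine whether they meet the criteria for acute serious bacterial infections (as described in Section 8.1.1, Serious Bacterial Infections), defining the" primary endpoint of the study. The synopsis says the same.
- Protocol 8.1.1: the DSMB is responsible for the review, to "determine whether they meet criteria for acute serious bacterial infections". The procedure is left to the DSMB Charter.
- SAP 2.2: the DSMB is to "determine whether they meet the criteria for acute serious bacterial infections (as described in protocol Section 8.1.1, Serious Bacterial Infections), defining the" primary endpoint.

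SAP 8.1.1 also defines the endpoint by diagnosis, according to "the criteria described in the relevant FDA (1) guidelines".

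SAP 8.1.2, which specifies the main analysis, derives the per-patient dataset from AE data. Its rule is: "The following terms will be searched in AE preferred term to determine if an acute serious bacterial infection occurred". Five labels follow: bacterial pneumonia, bacteremia/sepsis, bacterial meningitis, visceral abscess, and osteomyelitis/septic arthritis. The section mentions no DSMB result, no diagnostic criterion and no list of preferred terms. SAP section 12 declares no change from the protocol's planned analysis.

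**The concern.** The SAP gives two answers to the question of what counts as an event. Under SAP 2.2 it is what the DSMB confirms. Under SAP 8.1.2 it is what a search of coded terms returns. The programmer will follow 8.1.2.

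The two can disagree in both directions, because the essential features in protocol 8.1.1 are findings such as a positive blood culture or a new infiltrate, and a preferred term does not record them.

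The trial is single-arm and open-label, and its efficacy claim rests on this one count against a fixed threshold of 1.0. Missed events push the result towards success, and events that fail the criteria push it towards failure. Leaving two rules in place also allows a choice between two counts once the data are known.

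**Working it through.** **1. The criteria against the search rule**

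- *Sepsis.* Protocol 8.1.1 marks a positive blood culture as essential. An AE coded as sepsis without one would be found by the search and counted.
- *Pneumonia.* Under footnote d of protocol 8.1.1, "the finding of a new pulmonary infiltrate with consolidation on chest x-ray is considered sufficient" for counting an episode. Such an event need not be coded with the word *bacterial*, and a search for *bacterial pneumonia* would then miss it.
- *Abscess.* The visceral abscess entry names organ-specific forms: "elevated alkaline phosphatase concentration (hepatic abscess) pyuria in renal abscess", and also pancreatic abscess. None of these names contains *visceral abscess*.
- *Composite labels.* Two of the five labels join two conditions with a slash. With no mapping given, two programmers could obtain different counts.

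**2. Reproducing the plan's power**

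Inputs from SAP 3.6 and 8.1.2: N = 40, null rate 1.0 per year, true rate 0.49, one-sided alpha 0.01, Poisson counts, and success if the one-sided 99% upper limit is below 1.0. I take 40 patients as T = 40 patient-years.

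The SAP model is intercept-only with a log link, so its upper limit for x events is U(x) = (x/T) · exp(2.326/√x).

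- U(25) = 0.625 · exp(2.326/5) = 0.995: pass.
- U(26) = 0.650 · exp(2.326/5.099) = 1.026: fail.

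The boundary is therefore 25 events, and the exact Poisson test gives the same boundary.

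- Attained alpha: P(Poisson(40) ≤ 25) = 0.0076.
- Power: P(Poisson(0.49 · 40 = 19.6) ≤ 25) = 0.905.
- Normal approximation: Φ((√40 · 0.51 − 2.326)/√0.49) = 0.9005.

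The stated 90% is reproduced. One miscounted event moves the estimated rate by 1/40 = 0.025. At the planning rate the margin to the boundary is 25 − 19.6 = 5.4 events.

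**3. Effect of a miscount (assumed sizes)**

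Suppose the search finds a fraction c of true events, independently of one another, and the true rate is 1.0. The false-claim probability is P(Poisson(40c) ≤ 25).

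| Share missed | Mean count found | False-claim probability |
|---|---|---|
| 0% | 40 | 0.0076 |
| 5% | 38 | 0.017 |
| 10% | 36 | 0.035 |
| 20% | 32 | 0.123 |
| 30% | 28 | 0.327 |

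Suppose instead that the search inflates the count by a factor m at a true rate of 0.49. Power is P(Poisson(19.6m) ≤ 25).

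| Overcount | Mean count found | Power |
|---|---|---|
| 0% | 19.60 | 0.905 |
| 10% | 21.56 | 0.805 |
| 25% | 24.50 | 0.593 |
| 50% | 29.40 | 0.241 |

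**The case against.** The best defence is that SAP 8.1.2 is silent on the DSMB and does not reject its decisions. Protocol 8.1.1 requires every acute serious bacterial infection to be entered in the eCRF and leaves the adjudication procedure to the Charter. If DSMB decisions were written back to the AE record before the search ran, the two counts could agree. The Charter and the eCRF specification are not available, so this cannot be excluded. But nothing in the SAP says it happens, and 8.1.2 states that the search itself determines whether an event occurred. The Revision History says the programming process was added in response to FDA comments. That explains its origin without tying it to adjudication.

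Three further points have some weight.

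- The five labels may be meant as categories and not as literal strings. A hepatic abscess would then fall under visceral abscess, and the missed-event examples would weaken. The mapping would still be absent, and no mapping supplies a culture or X-ray result.
- SAP 5.6 lists incomplete laboratory work for the infection definition as a possible major deviation, and SAP 5.5 plans a per-protocol analysis of the primary endpoint. Neither adjudicates an event in the FAS count.
- Text after the SAP 8.1.3 outputs and in protocol 10.3 is blacked out and may hold a supportive analysis on confirmed events, so its absence cannot be claimed. It would not alter the visible main rule.

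With very few events the claim would survive a small miscount: 5 events in 40 patient-years give an upper limit of 0.35. The reported rate could still be wrong, and the plan's own assumption implies about 20 events.

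**Conclusion.** The concern holds. As written, SAP 8.1.2 decides the sole primary efficacy count by a rule that is not the determination the protocol and SAP 2.2 prescribe and that cannot apply the diagnostic criteria. The sample size calculation is sound; the fault lies in the source of the count.

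The direction of the error is not fixed. An assumed undercount of 10% to 30% takes the false-claim probability at a true rate of 1.0 from 0.8% to between 3.5% and 32.7%. An assumed overcount of 10% to 50% takes power at 0.49 from 90.5% to between 80.5% and 24.1%. These figures are illustrations that assume 40 patient-years, Poisson counts and miscount sizes for which the documents give no basis. The contradiction between the sections does not depend on them. It should be resolved before database lock.

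**What to change.** Rewrite the derivation in SAP 8.1.2 as follows.

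- The per-patient count is the number of distinct AE episodes that the DSMB determined to meet the protocol 8.1.1 criteria, with onset from the first infusion to the termination date.
- The preferred-term search serves only to find candidate AEs for DSMB review, in line with the Charter. It should use a predefined, broad list covering pneumonia, organ-specific abscesses, sepsis and bacteremia variants, meningitis, and bone and joint infections.
- Disagreements between search and DSMB are listed, and the search-based count is reported as a sensitivity analysis.

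The cost is a change of SAP wording, a term list, and one DSMB result variable merged into the analysis dataset. If DSMB decisions are not yet held as structured data, they must be recorded that way. The DSMB already makes these determinations under the protocol. Sample size, alpha, the 25-event boundary and power stay as they are.
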